or suctioning of secretions for the subsequent 15 to 30 minutes.(10–12,14,16,18,19) Patients were able to achieve goal trough levels using SL tacrolimus with minimal, if any, reported adverse effects. Published literature indicates the area under the blood-concentration-time curve (AUC) for SL tacrolimus is well correlated with whole blood trough levels, the current standard of care for therapeutic drug monitoring and guidance of dose adjustments to maintain concentrations within the desired therapeutic window.(11,12) In addition to serving as a safe and effective alternative to IV administration in patients who become intolerant of oral medications, the SL formulation offers advantages over PO tacrolimus as well. When administered orally, tacrolimus has poor bioavailability (approximately 25%) due to extensive first-pass metabolism and P-glycoprotein efflux.(20) These concerns are mitigated with SL administration, which allows for direct absorption into the blood. Avoidance of first-pass metabolism may also minimize the degree of interaction between tacrolimus and drugs that effect hepatic cytochrome P-450 enzymes.(18) Reduced doses with SL administration can also decrease pill burden and cost associated with tacrolimus use.(12,15,16) Studies undertaken to determine the optimal SL to PO dose conversion ratio in SOT patients report slightly variable results depending on the type of organ received,(10–12,14,16) with most centers recommending a ratio of 1:1 or 1:2.(17) Given that enteral and first-pass hepatic metabolism are bypassed with the SL route, one report suggests that a ratio of 1:1 be used when major drug interactions are present.(14)

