This study will be conducted in Rochester, Minnesota, where Mayo Clinic completes over 700 blood or marrow transplants per year, approximately 20% of which are allogeneic transplants. Around half of these will receive tacrolimus for GVHD prevention. As a referral center, patients are diverse with respect to diagnosis and demographics. Comprehensive care is provided by a multidisciplinary treatment team including physicians from a variety of medical specialties, advanced practice providers, pharmacists, nurses, dieticians, care coordinators and social workers. Integrated inpatient and outpatient care allows for close monitoring of patients throughout the care continuum, with near-daily appointments and twice weekly tacrolimus laboratory monitoring conducted locally through day +30 following transplant or longer, as dictated by a patient's medical course.

Identification of Study Subjects

Individuals will be identified from within the adult allogeneic BMT program at Mayo Clinic in Rochester, Minnesota. Participants will **include** adults prescribed tacrolimus for treatment or prevention of GVHD. Vulnerable populations, patients with contraindications to tacrolimus, inclusive of hypersensitivity, history of posterior reversible encephalopathy syndrome or calcineurin-inhibitor induced thrombotic microangiopathy, and those lacking the capacity to consent in English and declining to participate in research will be **excluded**.

Patients will be screened when scheduled for their pre-transplant pharmacist visit. Those meeting inclusion and exclusion criteria will be enrolled during a regularly scheduled pre-transplant clinic appointment. Here they will be supplied with HIPAA Authorization and consent forms. The consent form will describe the purpose of the study, the procedures to be followed, and the risks and benefits of participation. A copy will be given to each participant and this fact will be documented in the participant's record. Fifteen minutes, or additional time as necessary, will be allowed for discussion and patient questions. Patients will be informed their care will not be impacted by declining to participate in the study.

Definitions

Dose-adjusted conversion ratio of SL and PO tacrolimus (16):

- Calculated using the concentration-to-dose ratios for each route of administration
- $[(\text{Blood concentration}_{\text{SL}}/\text{daily dose}_{\text{SL}})/(\text{Blood concentration}_{\text{PO}}/\text{daily dose}_{\text{PO}})]$

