Patient report of barriers to administration of SL tacrolimus will be used to investigate feasibility of the SL formulation. These could include poor tolerability of the SL route, lack of understanding related to the administration instructions, or inability to refrain from eating or drinking for the defined amount of time. As described in "Study Procedure", these will be recorded at each clinic appointment when the patient sees a provider during the study timeframe. Per-protocol analysis will be conducted to determine the conversion ratio of SL and PO administration. Median dose conversion ratios will be compared between patients with new major drug interactions or undergoing dose changes of these medications and the remainder of the cohort.

We aim to include a total of 10 patients for analysis. This represents approximately 10% of the number needed to determine in future study the true conversion ratio with a 10% margin of error (n = 97 patients), assuming an estimated conversion ratio of 0.5 (extrapolated from available literature in the SOT population). Continuous data will be described using median (IQR). The conversion ratio of SL:PO administration of

tacrolimus will be calculated as described above for each patient (note that this is adjusted for the daily dose administered). Each subject will serve as his or her own control. The median will be determined for the cohort and by subgroup, as described in the paragraph above.

Data Storage

Data will be extracted from the EHR by select study personnel and stored in a password-protected Research Electronic Data Capture (REDCap) database. This platform meets the requirements of the Health Insurance Portability and Accountability Act of 1996 (HIPAA) compliance, with password protection and the ability to assign access levels that ensure tightly regulated data sharing. All source data will be de-identified so that only a unique study number bearing no relationship to personal identifiers will be used to identify participants. Only the investigators involved in the collection and analysis of the data will have access to information with individually identifiable private information about the human subjects. Reported data will be de-identified and presented only in composite form.

Potential Risks and Benefits to Patients

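### The n = 97 behind the pilot's sample size cannot be derived from what the plan states, and its likely formula does not fit a continuous ratio

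*Combined protocol and SAP*

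**What the plan says.** The sample-size statement is in Outcomes and Analysis: "We aim to include a total of 10 patients for analysis". The only reason given is that this is roughly a tenth of the "number needed to determine in future study the true conversion ratio with a 10% margin of error (n = 97 patients"). Apart from the margin, the plan names one input for that figure, a point value: "assuming an estimated conversion ratio of 0.5 (extrapolated from available literature in the SOT population"). No formula is named.

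The same section has the ratio calculated for each patient ("note that this is adjusted for the daily dose administered") and summarised by its median; "Continuous data will be described using median (IQR"). Under Definitions the ratio is "Calculated using the concentration-to-dose ratios for each route of administration": the sublingual (SL) concentration per daily dose divided by the oral (PO) concentration per daily dose.

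Background and Significance describes the earlier evidence on a dose scale: "Studies undertaken to determine the optimal SL to PO dose conversion ratio in SOT patients report slightly variable results". The same sentence then summarises practice across transplant programmes: "with most centers recommending a ratio of 1:1 or 1:2".

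**The concern.** A margin of error for a continuous quantity needs a measure of spread, a confidence level and a statement of whether the margin is absolute or relative. The plan gives none of these. It gives a point value of 0.5 and a margin of 10%, which are the inputs of a sample-size formula for a proportion. A conversion ratio is not a proportion: it is positive, is not capped at 1, and does not have variance p(1 − p).

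The scale of 0.5 is a second difficulty with the same calculation. An SL dose half the PO dose is 0.5 as a dose ratio, but the endpoint as defined would then be about 2 at equal concentrations.

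This is the plan's only sample-size calculation, and the pilot is meant to inform larger studies. A reader designing the next one could carry 97 forward as a justified target for 10% precision.

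**Working it through.** **Inputs from the plan.** Ratio 0.5, margin 10%, future n = 97, pilot n = 10 (10/97 = 10.3%), all from Outcomes and Analysis. The documents give no SD or CV, confidence level or margin type. Below, 95% two-sided confidence and every CV are assumptions.

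**Reproducing 97.**
- Single proportion, absolute margin 0.10: n = z²p(1 − p)/d² = 1.96² × 0.5 × 0.5 / 0.10² = 96.04, rounded up to 97.
- A second route gives the same number. For an arithmetic mean with a relative 10% margin and a CV of 50%, n = (1.96 × 0.5 / 0.10)² = 96.04, so 97 (99 with a t correction). It needs a CV that the plan does not state.

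The first route uses only the stated inputs and a conventional confidence level, so it is the likelier source. That remains an inference.

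**Does the proportion formula fit the endpoint?** At equal concentration C, the defined ratio is (C/D_SL)/(C/D_PO) = D_PO/D_SL. The 1:1 and 1:2 SL to PO dose ratios in the background therefore correspond to 1 and 2.
- At 1: p(1 − p) = 0, so n = 0.
- At 2: n = 1.96² × 2 × (1 − 2) / 0.10² = −768.

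The formula breaks down at both values.

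**What a continuous ratio would need.** Assume a lognormal ratio, with SD_log = √ln(1 + CV²). The n below is the smallest with t(0.975, n − 1) × SD_log/√n ≤ ln 1.10, that is, a geometric mean known to within ×/÷ 1.10.

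| Assumed CV | SD_log | n needed | 10 as share of n |
|---|---|---|---|
| 20% | 0.198 | 20 | 50% |
| 30% | 0.294 | 39 | 26% |
| 40% | 0.385 | 66 | 15% |
| 50% | 0.472 | 97 | 10% |
| 60% | 0.555 | 133 | 8% |
| 80% | 0.703 | 212 | 5% |

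The median, which is what the plan reports, needs about π/2 = 1.57 times as many patients (large-sample approximation under the same model). Conversely, 97 patients would give the geometric mean to ×/÷ 1.04 at a CV of 20% and ×/÷ 1.15 at 80%.

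**Margin type and scale.** For an arithmetic mean at a CV of 50% with an absolute margin of 0.10 (t-based), n = 27 if the mean ratio is 0.5 (SD 0.25) and n = 387 if it is 2 (SD 1.0).

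**What 10 patients give.** With t(9) = 2.262, the 95% confidence factor for the geometric mean is exp(2.262 × SD_log/√10): 1.23 at a CV of 30% and 1.40 at 50%. For the median, the 2nd to 9th ordered ratios cover it with probability 97.9%. The 95% limits for an SD from 10 patients are √(9/19.02) = 0.69 to √(9/2.70) = 1.83 times the estimate.

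**The case against.** The strongest reply is that nothing in this trial depends on 97. It refers to a later study, no test or decision uses it, the primary endpoint is feasibility, and the ratio is secondary and descriptive. The plan also describes 0.5 as an estimate extrapolated from another population, so 97 reads as a benchmark. All of that stands, and it keeps the point minor.

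Nor is 97 shown to be wrong. It is about right at a CV near 50%, and the plan never names the proportion formula. That also stands: the defect is lack of support, not a proven error in size or direction. It does not depend on which route was used, because one applies the wrong variance and the other needs an unstated CV.

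The scale of 0.5 could be called a separate question of definition. It does bear on how the trial's own ratio is read, but 0.5 is also an input to this calculation, so it belongs here too.

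Finally, the expected-precision figures for n = 10 rest on assumed CVs and a geometric mean, whereas the plan reports a median. That is fair: they should be labelled as illustrations, and an interval for the median is available. Leaving out a confidence interval is not in itself an error in a descriptive pilot.

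**Conclusion.** The concern holds, as a minor one. The plan attaches 10% precision to 97 patients, and its stated inputs cannot show this for a continuous ratio. The assumed 0.5 also does not match the plan's definition if it was taken from the 1:2 dose ratio. Under 95% confidence, a lognormal ratio and CVs of 20% to 80%, the number needed for a geometric mean within ×/÷ 1.10 runs from 20 to 212, so 97 may be too high, too low or about right. The range shows sensitivity to the assumed CV; it does not measure an error. Confidence is high that the inputs are missing and that p(1 − p) is not the variance of this endpoint. It is lower that the proportion formula was the one used. Enrolment, procedures, n = 10 and the primary endpoint are unaffected.

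**What to change.** **Minimum.** Delete the 97 and the statement that 10 is about a tenth of it, or keep 97 as provisional with its formula, CV, confidence level and margin type. Justify n = 10 as a feasibility pilot size and give its expected precision, labelled as resting on assumed CVs: a 95% interval for the geometric mean of about ×/÷ 1.23 at a CV of 30% and ×/÷ 1.40 at 50%. State whether 0.5 is SL dose over PO dose or the quotient under Definitions, and make the background, the definition and the sample-size statement agree. Cost: one sentence edited and one added on precision, plus the wording that identifies 0.5.

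**Recommended.** Beside the median (IQR), report a 95% confidence interval (t-based on the log scale for the geometric mean, or the 2nd to 9th ordered ratios for the median if all 10 patients are evaluable) and the SD of the log ratio. Say that the future sample size will be derived from that SD, naming the confidence level, margin type and summary (mean or median). Cost: two output values and one sentence, from data already collected, with no more patients, samples or visits.

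**Downsides.** The plan would no longer quote a fixed future target if 97 is deleted, and an SD from 10 patients is imprecise, so the future sizing should allow for its limits (0.69 to 1.83 times the estimate). With only 8 evaluable patients, the 2nd to 7th ordered ratios cover the median with probability 93.0%; reaching 95% would take the full range, with coverage 99.2%.

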**Use of sublingual tacrolimus in adult blood and
marrow transplant patients: a pilot study**

NCT# NCT04041219

16-MAY-2019

Department of Pharmacy
Research Proposal

Use of sublingual tacrolimus in adult blood and marrow transplant patients: a pilot study

Principal Investigator

[name]

Co-Investigators

[name]
[name]

Protocol Version: 2.0
Protocol Version Date: 16-May-2019

Abstract

Barriers to oral (PO) tacrolimus in recipients of an allogeneic blood or marrow transplant (BMT) are not uncommon and often result in reliance on intravenous (IV) tacrolimus, a formulation which is fraught with concerns. Sublingual (SL) administration of tacrolimus is widely used as a safe and effective alternative in the solid organ transplant population. Similar benefits may be appreciated by patients undergoing BMT, including avoidance of risks and expense associated with IV tacrolimus, as well as reduced pill burden and limited trough variability relative to PO tacrolimus. This study will establish feasibility and gather preliminary data on the dose conversion ratio of PO to SL tacrolimus through comparison of trough concentrations drawn during PO and SL tacrolimus delivery during routine laboratory monitoring. Results will be used to inform future studies in larger cohorts and assist in determining an accurate conversion ratio, which is imperative to inform clinician decision-making and allow for prescription of doses which result in trough levels that ensure the safety and efficacy of tacrolimus.

Specific Aims

- 1) Demonstrate feasibility of SL administration of tacrolimus in blood and marrow transplant (BMT) patients
- 2) Gather preliminary data to determine the conversion ratio of oral (PO) to sublingual (SL) administration of tacrolimus needed to achieve equivalent whole blood concentrations in BMT patients

Background and Significance

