Potential benefits to study participants include reduced pill burden and decreased intra-patient variability of trough levels, due to the ability of SL administration to bypass first-pass hepatic metabolism and drug efflux from the P-glycoprotein in the intestine. Significant scientific gains may be appreciated through demonstration of feasibility for this route of medication delivery. Initial data will illuminate a PO to SL conversion ratio which can be tested in a larger cohort of outpatients and extrapolated to environments in

which IV tacrolimus is currently used, most notably the peri-transplant period and inpatient environment. Determination of this ratio will improve clinicians' ability to prescribe doses that result in trough levels that ensure safety and efficacy when transitioning patients to SL tacrolimus.

Data Safety and Monitoring

The principal investigator (PI) or designated co-investigator will ensure screening was compatible with inclusion and exclusion criteria and confirm documentation of informed consent within 24 hours of patient enrollment. The PI or designated co-investigator will be informed of concerns by providers directing patient care as they occur and review records within 24 hours of notification. The PI will be responsible for ensuring participants' safety on a daily basis. This includes assuring routine trough monitoring for safety and efficacy is performed, weekly review of new records for potential adverse events related to SL administration of tacrolimus and reporting of serious adverse events and unanticipated problems to the Institutional Review Board (IRB).

References:

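### The SL:PO conversion ratio is to be reported only as a median (IQR) from 10 patients, with no confidence interval and no log-scale SD to inform the next study

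*Combined protocol and SAP*

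**What the plan says.** Outcomes and Analysis names feasibility as the primary endpoint and the dose-normalised SL:PO conversion ratio as the secondary endpoint. One ratio is calculated per patient, with each patient as his or her own control. The sample is small by design: "We aim to include a total of 10 patients for analysis". The planned summaries are "Continuous data will be described using median (IQR") and, for the ratio itself, "The median will be determined for the cohort and by subgroup, as described in the paragraph above". The subgroup split is by new or changed interacting drugs. No section mentions a confidence interval, a geometric mean, a log transformation or an SD.

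The same section justifies the 10 patients as about a tenth of what a later study would need for a "10% margin of error (n = 97 patients"), "assuming an estimated conversion ratio of 0.5 (extrapolated from available literature in the SOT population").

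On use of the result, the Abstract says: "Results will be used to inform future studies in larger cohorts". Potential Risks and Benefits to Patients speaks of initial data on a ratio to be tested in a larger cohort, and then says "Determination of this ratio will improve" clinicians' ability to prescribe. Data Storage limits reporting to de-identified, aggregate results.

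**The concern.** The plan's two numbers for the ratio are a location and a between-patient spread. Neither says how far the estimate from 10 patients might lie from the true value. A reader given only a median and IQR may take the median as settled.

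The second gap concerns planning. The size of a study that estimates a continuous ratio to a given margin depends on the variance of that ratio. The protocol gives no such variance, and the pilot is the natural place to obtain one. A ratio of two concentration-to-dose values is multiplicative, so the useful figure is the SD of the log ratio, and it is not among the planned outputs.

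**Working it through.** **Inputs.** From Outcomes and Analysis: 10 patients with one ratio each, a future n of 97, a 10% margin and an assumed ratio of 0.5. From Definitions: ratio = (concentration/daily dose on SL) ÷ (concentration/daily dose on PO). The confidence level is not stated; I assume 95% two-sided. No SD is stated; I use log-scale SDs of 0.3 to 0.6 as an illustrative range.

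**1. The plan's own figure.** With p = 0.5, d = 0.10 and z = 1.96:

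n = z² p(1 − p)/d² = 1.96² × 0.25/0.10² = 96.04, rounded up to 97.

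The figure reproduces, but with the formula for a binomial proportion. The variance in it is p(1 − p) = 0.25, which is not the variance of a continuous ratio.

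**2. What the future size depends on.** For a margin of ±10% on the fold scale, n = (1.96 × SD/ln 1.1)², with ln 1.1 = 0.0953:

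| Assumed log SD | n |
|---|---|
| 0.3 | 39 |
| 0.4 | 68 |
| 0.5 | 106 |
| 0.6 | 153 |

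The answer changes about fourfold across this range, so the log SD is the main planning figure the pilot could supply.

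**3. Uncertainty of the ratio at n = 10.** The 95% CI of the geometric mean is the estimate multiplied and divided by exp(t × SD/√10), with t = 2.262 on 9 df, that is exp(0.715 × SD):

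- SD 0.3: exp(0.215) = 1.24
- SD 0.4: exp(0.286) = 1.33
- SD 0.5: exp(0.358) = 1.43

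**4. A distribution-free interval for the median.** From the 2nd to the 9th ordered value, coverage is 1 − 2 × (1 + 10)/2¹⁰ = 1 − 22/1024 = 97.9%. The next narrower choice, 3rd to 8th, covers 89.1%. If the log ratios are normal, the 2nd-to-9th interval is on average about 1.44 times as wide as the t interval.

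**5. Precision of the SD itself.** The chi-square limits on 9 df are 2.700 and 19.02. The 95% limits are therefore √(9/19.02) = 0.69 and √(9/2.700) = 1.83 times the estimate. Sample size goes with the square, so a size built on this SD could be off by a factor of 0.47 to 3.3.

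**6. Direction of the ratio.** Suppose the troughs are equal and the SL dose is half the PO dose. The formula in Definitions then gives (C/0.5D) ÷ (C/D) = 2. The sample-size paragraph assumes 0.5. The widths in step 3 are the same in either direction, but the position of the interval relative to 1:1 or 1:2 is not.

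**The case against.** Median (IQR) is a conventional summary for 10 observations in a pilot whose primary endpoint is feasibility. The protocol calls the ratio preliminary and leaves the true value to a later study. The per-patient ratios will be held in the study database, so the investigators could compute a log SD at any time, and a reader could back out a rough one as ln(Q3/Q1)/1.349. All of this is fair and keeps the point modest. The back-calculation is a poor substitute, however. Under normality at n = 10, with a common quartile rule, it averages about 13% too low and has a coefficient of variation of 36%, against 24% for the sample SD.

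At n = 10 the IQR also happens to be close in width to the CI: for log-normal ratios the quartiles lie at a factor of exp(0.6745 × SD) around the median, against exp(0.715 × SD) for the CI. That is a coincidence of this sample size. It fails in the subgroups, where the CI widens and the IQR does not.

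Two stronger readings are tempting, and the documents support neither.

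- **A reader might infer that the median wastes precision.** It has 72% of the efficiency of the mean at n = 10 if the log ratios are normal, but no distribution is given. Outliers are plausible: one trough per route can suffice, doses are discretionary, and interacting drugs may start or change. By simulation, if 10% of values have three times the SD, the median is about 11% more efficient than the mean; with t tails on 4 df it is about 19% more efficient.
- **A reader might infer that the pilot cannot tell 1:1 from 1:2.** Separating them is not a stated aim; they appear in Background and Significance as solid-organ practice. Nor would 10 patients necessarily be too few. If the true factor is 2, a log-scale 95% CI excludes 1 with a chance of 97% at a log SD of 0.5 and 90% at 0.6. An estimate exactly midway has a CI covering both candidates only from a log SD of 0.484 (ln 2/2 ÷ 0.715), which is the least favourable placing.

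**Conclusion.** The point holds as an omission of moderate weight. Followed as written, the plan reports a conversion ratio from 10 patients without any statement of its uncertainty, and it does not name the log SD that a later precision-based study would need.

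The factors of 1.24 to 1.43 are illustrations. They rest on assumed log SDs of 0.3 to 0.5 and roughly normal log ratios. The 97.9% coverage needs only independent patients and a continuous distribution. The limits of 0.69 and 1.83 for the SD assume normal log ratios and show that the pilot's SD will be an imprecise planning input, though still better than none.

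No interval can be interpreted against 1:1 or 1:2 until the direction of the ratio is reconciled. Nor does an interval remove bias from the fixed order, SL first and PO second.

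**What to change.** In Outcomes and Analysis, keep the median (IQR) and add:

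1. The geometric mean ratio with a t-based 95% CI, from the logs of the per-patient ratios.
2. The SD of the log ratio with its 95% CI, named as a planning input for the next study, with a note that at n = 10 the limits are about 0.69 to 1.83 times the estimate.
3. The distribution-free interval for the median, 2nd to 9th ordered values (97.9% coverage), in case outliers make the median the better estimator.

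The ranks in item 3 and the multipliers in item 2 are for exactly 10 evaluable patients and should be recalculated if the number differs. Give the range of the ratios rather than a patient-by-patient listing, which would conflict with the commitment in Data Storage to aggregate reporting.

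Reconcile the formula in Definitions with the assumed 0.5 in the sample-size paragraph, and state the direction wherever the ratio is reported.

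The cost is a few lines of analysis text, with no extra patients, samples or visits. The downside is that the reported ratio will look less certain.
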